5.2.6.1.4 Adverse events of special interest

No adverse events of special interest have been defined and no DILI procedures are required for this trial as alteplase is a marketed product with well-known safety profile.

5.2.6.1.5 Intensity (severity) of Adverse events

The intensity (severity) of the AE should be judged based on the following:

Mild:	Awareness of sign(s) or symptom(s) that is/are easily tolerated.
Moderate:	Sufficient discomfort to cause interference with usual activity.
Severe:	Incapacitating or causing inability to work or to perform usual activities.

5.2.6.1.6 Causal relationship of adverse events

Medical judgement should be used to determine whether there is a reasonable possibility of a causal relationship between the adverse event and the given study treatment, considering all relevant factors, including pattern of reaction, temporal relationship, de-challenge or re-challenge, confounding factors such as concomitant medication, concomitant diseases and relevant history.

Arguments that may suggest that there is a reasonable possibility of a causal relationship could be:

- The event is consistent with the known pharmacology of the drug.
- The event is known to be caused by or attributed to the drug class.
- A plausible time to onset of the event relative to the time of drug exposure.
- Evidence that the event is reproducible when the drug is re-introduced.
- No medically sound alternative aetiologies that could explain the event (e.g. pre-existing or concomitant diseases, or co-medications).
- The event is typically drug-related and infrequent in the general population not exposed to drugs (e.g. Stevens-Johnson syndrome).
- An indication of dose-response (i.e. greater effect size if the dose is increased, smaller effect size if dose is reduced).

Arguments that may suggest that there is no reasonable possibility of a causal relationship could be:

- No plausible time to onset of the event relative to the time of drug exposure is evident (e.g. pre-treatment cases, diagnosis of cancer or chronic disease within days/weeks of drug administration; an allergic reaction weeks after discontinuation of the drug concerned).

- Continuation of the event despite the withdrawal of the medication, taking into account the pharmacological properties of the compound (e.g. after 5 half-lives). Of note, this criterion may not be applicable to events whose time course is prolonged despite removing the original trigger.
- Additional arguments amongst those stated before, like alternative explanation (e.g. situations where other drugs or underlying diseases appear to provide a more likely explanation for the observed event than the drug concerned).
- Disappearance of the event even though the trial drug treatment continues or remains unchanged.

5.2.6.2 Adverse event collection and reporting

5.2.6.2.1 Adverse event collection

The investigator shall maintain and keep detailed records of all adverse events in the patient files. The following must be collected and documented on the appropriate eCRF(s) by the investigator:

- From signing the informed consent onwards until the individual patient's end of trial (the End of Study (EOS) Visit):
all adverse events (serious and non-serious).
- After the individual patient's end of trial:
the investigator does not need to actively monitor the patient for new adverse events but should only report any occurrence of cancer and trial treatment related serious adverse events of which the investigator may become aware of by any means of communication, e.g. phone call. Those adverse events should be reported on the BI SAE form (see [Section 5.2.6.2.2](#)), but not on the eCRF.

The rules for Adverse Event Reporting exemptions still apply, please see [Section 5.2.6.2.4](#).

5.2.6.2.2 Adverse event reporting to the sponsor and timelines

For the patients on Alteplase treatment arm, the investigator must report serious adverse events, and non-serious adverse events which are relevant for the reported SAE on the BI SAE form via fax (except of Russia where SAE form is to be send via Clinergize) immediately (within 24 hours) to the sponsor's unique entry point (country-specific contact details will be provided in the ISF). The same timeline applies if follow-up information becomes available. In specific occasions, the investigator could inform the sponsor upfront via telephone. This does not replace the requirement to complete and fax the BI SAE form.

With receipt of any further information to these events, a follow-up SAE form has to be provided. For follow-up information the same rules and timeline apply as for initial information. All serious and adverse events, including those persisting after individual patient's end of trial must be followed up until they have resolved, have been assessed as "chronic" or "stable", or no further information can be obtained.

For patients not exposed to Alteplase treatment, but to SOC only: No expedited reporting via SAE form is required. All safety data (AEs and SAEs) should be included in the eCRF.

Consequently, the investigator is encouraged to report all adverse events for SOC group drugs in accordance to the local regulatory requirements for spontaneous AE reporting at the investigator's discretion by using their locally established routes and AE report forms.

5.2.6.2.3 Pregnancy

Not applicable for this trial. This trial will exclude pregnant women, and patients are severely ill during the observation period of the trial. To rule-out potential pregnancy urine pregnancy test is performed during screening and at Day 28. A woman is considered of childbearing potential, i.e. fertile, following menarche and until becoming post-menopausal unless permanently sterile. Permanent sterilisation methods include hysterectomy, bilateral salpingectomy and bilateral oophorectomy. Tubal ligation is NOT a method of permanent sterilisation.

A postmenopausal state is defined as no menses for 12 months without an alternative medical cause.

5.2.6.2.4 Exemptions to SAE reporting

Disease progression of the underlying ARDS reflects the natural course of the disease and is exempted from reporting as an (S)AE. Progression of the subject's underlying ARDS will be recorded on the appropriate pages of the (e)CRF only and will not be reported as an SAE. The specific preferred terms (PTs) that are exempt are:

- Acute respiratory distress syndrome
- Respiratory distress
- Acute respiratory failure
- Respiratory failure

Death due to disease progression is also to be recorded on the appropriate eCRF page and not on the SAE form. Disease progression and death due to disease progression will therefore not be entered in the safety database and hence not get expeditiously reported.

However, if there is evidence suggesting a causal relationship between the study drugs and the progression of the underlying ARDS, the event must be reported as SAE on the eCRF, as well as on the SAE form.

Exempted events will be monitored at appropriate intervals by the external DMC.

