The most common AEs by system organ class were: respiratory, thoracic and mediastinal disorders (alteplase 0.3/0.02 mg/kg: 7 patients/35.0%, alteplase 0.6/0.04 mg/kg: 12 patients/60.0%, SOC: 9 patients/40.9%), infections and infestations (9 patients/45.0%, 4 patients/20.0%, 11 patients/50.0%), and general disorders and administration site conditions (7 patients/35.0%, 7 patients/35.0%, 4 patients/18.2%).

Serious AEs reported for >2 patients in a treatment group were respiratory failure (alteplase 0.3/0.02 mg/kg: 2 patients/10.0%, alteplase 0.6/0.04 mg/kg: 0 patients, SOC: 6 patients/27.3%), pulmonary embolism (2 patients/10.0%, 3 patients/15.0%, 1 patient/4.5%), septic shock (1 patient/5.0%, 0 patients, 4 patients/18.2%), and epistaxis (3 patients/15.0%, 1 patient/5.0%, 0 patients).

Treatment-emergent bleeding events were more frequent in the alteplase treatment groups, both for any bleeding events and major bleeding events. Major bleeding events up to Day 6 were reported only in the alteplase treatment groups (1 patient in the 0.3/0.02 mg/kg dosing group and 4 patients in the 0.6/0.04 mg/kg dosing group). Most bleeding events until Day 12 were non-major (4 patients, alteplase 0.3/0.02 mg/kg; 9 patients, alteplase 0.6/0.04 mg/kg; 3 patients, SOC group). There were no fatal bleeding events.

The study results of Part 1 support the continuation of the study into Phase III (Part 2), implementing a comparison of the alteplase 0.6/0.04 mg/kg dose versus SOC alone.

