5.2.6 Assessment of adverse events

5.2.6.1 Definitions of adverse events

5.2.6.1.1 Adverse event

An adverse event is defined as any untoward medical occurrence in a patient or clinical investigation patient administered a medicinal product and which does not necessarily have to have a causal relationship with this treatment.

An adverse event can therefore be any unfavourable and unintended sign (including an abnormal laboratory finding), symptom, or disease temporally associated with the use of a medicinal product, whether or not considered related to the medicinal product.

The following should also be recorded as an adverse event in the eCRF and BI SAE form (as applicable):

- Worsening of the underlying disease or of other pre-existing conditions
- Changes in vital signs, ECG, physical examination and laboratory test results, if they are judged clinically relevant by the investigator.

If such abnormalities already exist prior to trial inclusion, they will be considered as baseline conditions and should be collected in the eCRF only.

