7.2 PLANNED ANALYSES

7.2.1 General considerations

With regards to each efficacy and safety endpoint, the term "baseline" refers to the last observed measurement prior to randomisation for all patients.

The statistical analysis will be based on the following populations:

The Randomised Set (RS) will consist of all randomised patients.

The Full Analysis Set (FAS) will consist of all randomised patients with at least one baseline and one post baseline assessment relating to the primary endpoint of interest - refer to [Section 2.1.2](#) for primary endpoints related to Part 1 and Part 2.

The Treated Set (TS) will consist of all patients who were randomised and, for patients in the alteplase groups, treated with at least one dose of trial drug.

Per Protocol Set (PPS) will consist of all patients in FAS who were without important protocol deviations (IPDs) for efficacy. The definition of IPDs will be specified in the Trial Statistical Analysis Plan (TSAP) but this PPS will only be determined for Part 2.

All endpoints will be presented for Parts 1 and Part 2 separately, and at the end of Part 2 most endpoints will additionally be pooled for descriptive purposes.

All analyses for all endpoints, both inferential and descriptive, including safety, will be performed on the NIV patient cohort, and the IMV patient cohort separately. This is in line with the statistical objectives of the study.

For selected endpoints, if homogeneity between the two patient cohorts is observed, combined treatment estimates will be determined using suitable meta-analysis techniques. These will be outlined in more detail in the Trial Statistical Analysis Plan.

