7.8.1 Adverse Events

Unless otherwise specified, the analyses of AE will be descriptive in nature. All analyses of AEs will be based on the number of subjects with AEs and NOT on the number of AEs.

AEs will be coded using the most recent version of the Medical Dictionary for Regulatory Activities (MedDRA) coding dictionary

The analysis of AEs will be based on the concept of treatment emergent adverse events (TEAE). That means that all adverse events occurring 'on treatment' as outlined in [Section 6.7](#) will be considered as TEAE.

All AEs occurring before 'on treatment' will be assigned to 'screening' and all AEs occurring after 'on treatment' will be assigned to 'post-treatment'. In general, AEs attributed to 'Screening' or 'Post-treatment' will be listed only.

An overall summary of AEs will be presented.

Frequencies [N (%)] of patients with AEs will be summarised by treatment, primary system organ class and preferred term (using MedDRA). Separate tables will be provided for patients with serious adverse events.

The system organ classes will be sorted according to the standard sort order specified by European medicines agency (EMA), preferred terms will be sorted by frequency (within system organ class).

Additionally, the following analyses will be reported for disclosure on European Union Drug Regulating Authorities Clinical Trials Database (EudraCT) and clinicaltrials.gov:

- Frequency [N(%)] of patients with non-serious AEs occurring with incidence in preferred term greater than 5% by treatment,
- AEs per arm for disclosure on EudraCT by treatment
- Non-serious AEs for disclosure on EudraCT by treatment
- Serious AEs for disclosure on EudraCT by treatment

Adverse events of interest

All endpoints related to safety, outlined in [Section 5.2.2](#) and [Section 5.3](#), are clearly marked as such, in particular, endpoints related to MBE, Stroke, MI, PE and DVT. There is no further description below on how they should be analysed, however, they will be summarized with the safety data under the topic of 'AEs of special interest'.

There are two other AEs of special interest, which are not mentioned in [Sections 5.2.2](#) and [5.3](#):

- Transient ischemic attack
- Systemic embolism

AEs recorded on the AE page of the CRF, indicated as such via the relevant tick box, will be grouped and summarized using frequency tables.

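### By-arm AE and SAE tables cannot be read as a comparison for four ARDS-progression terms, because these enter the SAE data through a drug-attribution route that in practice exists only on alteplase

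*Protocol*

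**What the plan says.** Protocol 5.2.6.2.4 sets the exemption for all subjects: "Disease progression of the underlying ARDS reflects the natural course of the disease and is exempted from reporting as an (S)AE". It lists four preferred terms (ARDS, respiratory distress, acute respiratory failure, respiratory failure). Progression "will be recorded on the appropriate pages of the (e)CRF only and will not be reported as an SAE", and "Disease progression and death due to disease progression will therefore not be entered in the safety database". The exception applies "if there is evidence suggesting a causal relationship between the study drugs and the progression of the underlying ARDS"; the event must then be reported as an SAE on both the eCRF and the SAE form. Exempted events are monitored by the external DMC (also Protocol 8.7).

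Protocol 5.2.6.1.1 names, among items that should be recorded as adverse events where applicable, "Worsening of the underlying disease or of other pre-existing conditions", without mentioning the exemption. Protocol 5.2.6.2.2 asks that all AEs and SAEs of SOC patients go into the eCRF, again without mentioning it. Sections 5.2.6.2.1 and 8.4 and flow chart footnote 14 do state that the exemption stays in force, and 5.2.6.1.3 points to it.

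Part 2 SAP 7.8.1 plans that "Frequencies [N (%)] of patients with AEs will be summarised by treatment, primary system organ class and preferred term", with separate tables for serious events and tables for registry disclosure. Its visible text has no table of exempted events and no caveat.

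In Part 1, before Global Amendment 2 introduced the exemption, these events were reported as serious: "Serious AEs reported for >2 patients in a treatment group were respiratory failure", and the list continues with other events (Protocol 1.1). Protocol 7.2.1 adds that "at the end of Part 2 most endpoints will additionally be pooled for descriptive purposes".

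**The concern.** A by-arm table is comparable only if the rule that puts an event into it works the same way in both arms. Here entry depends on attribution to a drug that one arm does not receive, judged by investigators who know the allocation. The same respiratory failure can be an SAE on alteplase and has no equivalent route on SOC. The missing cross-references add a second source of difference: a site that works from 5.2.6.1.1 or 5.2.6.2.2 may put progression on the AE page, while a site that works from 5.2.6.2.4 does not.

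Respiratory safety is a live question. In Part 1, adverse events in the respiratory system organ class were reported in 60.0% on the dose carried forward and 40.9% on SOC, while respiratory failure as an SAE ran the other way. A reader of the Part 2 tables would want to know which pattern held.

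**Working it through.** No planned figure is in dispute, so the check is mainly a trace of the recording rules. The arithmetic only gives scale.

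**Part 1 figures.** The denominators follow from the percentages in Protocol 1.1: 2/0.10 = 20 (low dose), 3/0.15 = 20 (dose carried forward, from its pulmonary embolism entry) and 6/0.273 = 22 (SOC). Respiratory failure as an SAE was therefore 2/20 = 10.0%, 0/20 = 0% and 6/22 = 27.3%, as printed. These events are common enough for the recording rule to matter.

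**Trace of the rule.**
- Protocol 5.2.6.1.6 judges causality against the study treatment given.
- Protocol 5.2.6.2.2 describes SOC patients as not exposed to alteplase and requires no SAE form for them.
- Protocol 4.1.5.1 confirms that site staff are not blinded.

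No sentence says the exception is for alteplase only. It follows because SOC patients have no study drug to which progression could be linked.

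**What the SAE table can show for the four terms.** Let p be the true incidence, a the share of alteplase cases attributed to drug, and 140 and 70 the planned NIV arm sizes (Protocol 7.5).

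| Situation | Alteplase | SOC |
|---|---|---|
| Exemption followed everywhere, no case attributed | 0 | 0 |
| Exemption followed everywhere, share a attributed | 140 × p × a | 0 |
| Some sites record worsening under 5.2.6.1.1 or 5.2.6.2.2 | depends on site | depends on site |

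**Illustration of the second row.** The ranges are assumptions, not in the documents: p from 10% to 27.3%, equal in both arms, and a from 0% to 25%. The tabulated difference is p × a; the true difference is 0.
- a = 0: both arms show 0.
- p = 0.10, a = 0.25: 140 × 0.10 = 14.0 true alteplase cases, of which 14.0 × 0.25 = 3.5 are tabulated. On SOC, 0 of 70 × 0.10 = 7.0. Apparent excess 2.5 points.
- p = 0.273, a = 0.25: 140 × 0.273 = 38.2 true alteplase cases, of which 38.2 × 0.25 = 9.6 are tabulated. On SOC, 0 of 70 × 0.273 = 19.1. Apparent excess 6.8 points.

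**Can the sign reverse?** Assume a true 10% on alteplase and 27.3% on SOC, a difference of −17.3 points. With 5% to 25% attributed, the table shows 0.10 × 0.05 = +0.5 to 0.10 × 0.25 = +2.5 points. Under those assumptions a true benefit would appear as a small harm.

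**The case against.** The strongest reply is that the exemption is clear, applies to both arms and is repeatedly kept in force. A reader might infer that 5.2.6.1.1 requires worsening always to be recorded and so contradicts 5.2.6.2.4 outright. The text does not support that: it is a recommendation qualified by applicability, and 5.2.6.2.1, which governs collection, preserves the exemption. What stands is a general rule beside a specific exemption with two cross-references missing. Variation between sites is possible, not shown.

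A reader might also infer that the events are lost, or that the trial cannot assess respiratory harm. Neither follows. The events go on eCRF pages and to the DMC. The daily WHO scale, intubation and extubation times, treatment failure and mortality capture deterioration in both arms whatever the attribution. These measures do not replace a count by term, however. Treatment failure uses the last known status up to Day 28 (Part 2 SAP 5.2.1), so it misses a patient intubated and weaned before then, or respiratory failure managed without intubation. DMC review is not a planned table.

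Finally, Part 2 safety analysis is descriptive (Protocol 7.2.5), and not everything can be seen. SAP 5.3, the sponsor's AE-handling standards, the CRF and the separate plan for pooled analyses are not available. The absence of a table is therefore established only for the visible text.

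**Conclusion.** The point holds in a limited form. For the four exempt terms, the by-arm AE and SAE tables in the visible Part 2 SAP cannot be read as a between-arm comparison. If the exemption is applied uniformly and nothing is attributed, they show zero in both arms, which is uninformative but not skewed. If some cases are attributed, the skew runs against alteplase: 0 to 6.8 points under the assumed ranges when the true difference is nil. If sites follow different sections, the direction cannot be predicted.

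This rests on two readings: that the exception cannot in practice be triggered on SOC, and that the eCRF pages meant in 5.2.6.2.4 are not the AE page from which the standard tables are built.

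A reader might project the Part 1 SOC rate forward and conclude that about 19 of 70 SOC patients (0.273 × 70 = 19.1) will be missing from the SAE table. The documents do not support that as a forecast. The rate comes from 22 patients (exact 95% interval roughly 11% to 50%) in a part that mixed NIV and IMV patients, under D-dimer and fibrinogen criteria that have since changed. Nor do they show that adverse events of the two parts will be pooled: Protocol 7.2.1 speaks of most endpoints. Pooling would mix two recording rules only if it is done.

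**What to change.** 1. In Protocol 5.2.6.1.1 and 5.2.6.2.2, add a cross-reference to the exemption in 5.2.6.2.4, so that one recording rule applies at all sites and in both arms.
2. In Part 2 SAP 7.8.1, add a by-arm table of the four exempt terms and of deaths due to progression, regardless of causality. Build it from the eCRF pages where they are recorded plus any AE-page entries, over the same window in both arms. The on-treatment window in SAP 6.7 does not serve as it stands: it starts at randomisation on SOC but at first dose on alteplase, and can run longer on alteplase. Show the standard AE and SAE tables with and without these terms, or with a caveat.
3. If Part 1 and Part 2 safety data are pooled, apply the same inclusion rule for these terms to both parts.

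Expedited reporting of attributed cases is unchanged. The cost is two short cross-references and one or two extra tables, using events the protocol already requires to be recorded. The CRF should be checked to confirm that the pages identify the four terms and their dates.

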5.3 DRUG CONCENTRATION MEASUREMENTS AND PHARMACOKINETICS

5.3.1 Assessment of pharmacokinetics

Participation in PK sampling is voluntary and not a prerequisite for participation in the trial. PK sampling will only occur after a separate PK informed consent has been given in accordance with local ethical and regulatory requirements. It is intended to obtain PK samples from at least 10 patients per dose group in Part 1. As PK samples collection included less than 10 patients per treatment arm in Part 1, collection of PK samples will continue in Part 2. It is intended to obtain PK samples from at least 17 patients receiving Alteplase in Part 2.

Three samples per patient will be collected:

- 1st sample: prior to first drug administration on Day 1 (Visit 2a pre-dose) (planned time: -1:00 h; time window -2:00 h to just prior drug administration)
- 2nd sample: at steady state of the initial i.v. infusion on Day 1 (Visit 2a post-dose initial i.v. infusion) (planned time 1:30 h; time window: between 1 h after start of initial i.v. infusion and just prior to end of initial i.v. infusion)
- 3rd sample: at steady state of the long-term i.v. infusion on Day 1 (Visit 2a post-dose long-term i.v. infusion) (planned time: 6:00 h; time window: between 2 h after start of long-term i.v. infusion and just prior to end of long-term i.v. infusion)

[figure not shown]
The actual sampling date and time for blood samples will be reported in the eCRF. To allow a valid PK analysis, it is of utmost importance to document the exact clock time of start/end of infusion and blood sample collection. Every attempt should be made to adhere to a constant infusion rate of approximately 1 hour prior to drawing of sample 2 and approximately 2 hours prior to drawing of sample 3.

